### **Statistical Analysis Plan**

All effectiveness analyses for the primary (PHQ-9) and secondary clinical (GAD-7, suicidal ideation) outcomes will use intention to treat methods. A comparison of population characteristics (race and ethnicity, age, gender, health status, baseline depression and use of other mental health treatments) must be made between patients receiving TES and the control treatment. Should the populations be different, propensity scores will be estimated for the likelihood of receiving TES, and models will adjust for those scores (trimming the data as necessary). After the population comparison and appropriate adjustment, we will compare overall effectiveness, using generalized linear mixed models (GLMM) to determine if there are differences in effectiveness between individuals receiving TES and CT over time. Separate models will be run for PHQ-9 and GAD-7, using participants who meet entry criteria for each (PHQ-9 > or = 10 or GAD-7 > or = 8, respectively). Missing data will be managed through multiple imputation. Additional covariates will also be included to identify any substantive changes in the service, technologies, and/or implementation plan as a result of optimization during the trial. Moderation of TES on effectiveness. Moderation of patient characteristics (race, ethnicity, income, age, sex, health status, substance/alcohol use, or use of other mental health treatments, including pharmacologic) will be analyzed in individual GLM models by estimating a treatment by moderator interaction in predicting end of treatment depression scores adjusting for baseline levels of depression.

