This patient app, called Vira (which is a product developed and managed by Ksana Health), will be evaluated with patients receiving care from Rush University Medical Center's primary care and family medicine clinics, which serve racially, ethnically, and economically diverse communities. The TES will include a service protocol that defines how a coach will interact with the patient around these sensed behavior targets, a coach dashboard that provides visibility into app use and patient status, and tools that enable coach communication with the patient to provide support. Thus, we will evaluate a TES that can support depression and/or anxiety care in general medicine, with a unique innovation focus on patient-facing features that harness emerging personal sensing methods to support behavior change in patients with depression. To achieve these goals, we have the following 3 aims:

Aim 1: Design Study (completed in years 1-2 of the project period): Design and develop a TES for patients receiving care in a primary care/family medicine setting that harnesses personal sensing technologies. A TES for depression has been designed, developed, and refined with input from key stakeholders including patients, staff, physicians, and others identified during the design process. User-centered design (UCD) principles were used to design the technology, service protocol (e.g., intervention and coordination protocols), and an implementation plan. Design efforts focused on the integration of personal sensing technologies.

Aim 2: Randomized Clinical Trial. Pilot the feasibility of an Optimization, Effectiveness, Implementation (OEI) Hybrid trial of the TES. The OEI Hybrid trial extends the hybrid (type 1)

STU#:00211887

effectiveness-implementation trial³⁰ design by allowing optimization of the TES technology, service protocol, and implementation plan to the delivery context.^{31,32} The TES will be compared to a control treatment (CT) app that provides basic psychoeducation.

Sub-aim 2.1 Effectiveness. The primary outcomes are patients' depression severity (PHQ-9)³³, and anxiety severity (GAD-7)³⁴. The secondary outcome is quality of life (PedsQI). Patient characteristics (race, ethnicity, income, age, health status, substance and alcohol use, other mental health treatment [including pharmacological]), stigma, discrimination, and mobile phone use will be examined as moderators.

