Participants randomized to the CT condition will use an app designed by researchers at the University of Virginia to deliver psychoeducational content to help people self-manage symptoms of stress, depression and anxiety. The mood education app will be cloned by Audacious Software for use in this study and data will be hosted on Northwestern University Feinberg School of Medicine's AWS environment.

RCT PROCEDURES INVOLVED

We will utilize an RCT based on our OEI hybrid trial design. A total of 130 Rush Patients will be randomized to either TES or Control Treatment (CT). Depressive and anxiety symptoms and other outcomes will be measured at baseline, 4, 8, and 12 weeks. Beyond 12 weeks, participants will be allowed to continue use of the apps for the study duration, though the TES coaching service will be discontinued at the end of 8 weeks. App use will be tracked for the entire study duration. Should a patient begin treatment but stop engaging, a single question survey will be administered to gauge the reason why and potentially optimize treatment as a result of the feedback.

Patient populations will be all Rush patients who are 13+ years old who are experiencing at least moderate symptoms of anxiety and/or depression and are open to using a smartphone app to get mental health support. Out of the total number of participants, 10%, or approximately 13 patients are expected to be adolescents.

All participant management will be performed by personnel at Northwestern University, and Rush.

Assessment Strategy for Sub-aim 2.1 Effectiveness

The primary outcomes are depressive symptom severity, measured using the PHQ-9³³, and anxiety symptom severity, measured by the GAD-7. Administration will occur as part of the research protocol via REDCap online, or if not feasible via phone.¹⁰¹ Secondary outcomes include quality of life. Primary and secondary outcome data will be gathered from patients as outlined in Table 1 below.

Table. 1: Primary and Secondary Outcome Measures

Outcome/Construct	Measure	Method	Timing	Type
Depressive symptoms	PHQ-9	Self-report Survey	0w, 4w, 8w, 12w	Primary
Anxiety symptoms	GAD-7	Self-report Survey	0w, 4w, 8w, 12w	Primary
Quality of Life	PedsQL	Self-report Survey	0w, 4w, 8w, 12w	Secondary

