of engagement relative to the CT, with by testing the mediational effects of subjective and objective engagement with the apps on the primary outcomes, depression (PHQ-9) and anxiety (GAD-7). Subjective engagement will be measured using the Twente Engagement with eHealth Technologies Scale (TWEETS), while objective engagement will be measured by app use (number of app launches and time from first to last use). We hypothesize that the difference between the TES and CT will be mediated by subjective and objective engagement. We also hypothesize the moderating effects of patient characteristics on subjective and objective engagement, depression, and anxiety will be lower in the TES arm, relative to CT, as a result of inclusion of users' voices through the design processes used in the creation of the TES app.

Mediation will be tested using methods by Iacobucci.¹²¹ Using analogous adaptations of methods to Preacher's methods,^{122,123} we will be able to test for moderation and mediation together. Between patient characteristics and actionable targets (subjective and objective use) we could test many moderated mediation (conditional indirect effects) which may indicate that a particular subset of participants (defined by subjective or objective use, and patient characteristics) may be more likely to benefit from TES. Multiple models will need to be fit, increasing the possibility of an inflated type I error. To prevent this, we will implement a false discover rate (FDR) control using methods by Benjamini-Hochberg¹²⁴ although as these are pilot studies, we will test these models at a FDR of 10%. Depending on the distribution of the variables under consideration, we will fit linear or logistic regression models to estimate regression parameters a (TES and the relationship to potential mediators) and b (mediator relationship to the outcome). Iacobucci shows that a normally distributed test statistic can be constructed from standardized regression parameters $Z_a = a/SE_a$ such that $Z(\text{mediation}) = Z_a * Z_b / (\sqrt{Z_a^2 + Z_b^2 + 1})$ can be used to test for mediation. Further, we can examine if there is further moderation of these models such that any patient covariate could moderate the relationship between TES use and depression outcomes. Power analyses for the individual RPs can be found in the RPs.

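### GAD-7 is a primary outcome in three parts of the protocol but secondary in its analysis section and the SAP, and nothing says which label governs

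*SAP*

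**What the plan says.** **GAD-7 as primary.** Protocol Sub-aim 2.1 lists depression severity on the PHQ-9 "and anxiety severity (GAD-7" as the primary outcomes. The assessment strategy for that sub-aim pairs PHQ-9 depression severity "and anxiety symptom severity, measured by the GAD-7", and Table 1 marks both scales Primary. The Aim 3 analysis tests mediation "on the primary outcomes, depression (PHQ-9) and anxiety (GAD-7".

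**GAD-7 as secondary.** The protocol's Data Analysis section on Effectiveness and the SAP share one sentence: "All effectiveness analyses for the primary (PHQ-9) and secondary clinical (GAD-7, suicidal ideation) outcomes will use intention to treat methods".

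**Secondary outcomes.** Sub-aim 2.1 says "The secondary outcome is quality of life (PedsQI", and Table 1 agrees (PedsQL). The Data Analysis section and the SAP do not mention it. They name suicidal ideation, which is in neither Sub-aim 2.1 nor Table 1.

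**Models and timing.** "Separate models will be run for PHQ-9 and GAD-7, using participants who meet entry criteria for each". "Depressive and anxiety symptoms and other outcomes will be measured at baseline, 4, 8, and 12 weeks", and the main mixed model is fitted "to determine if there are differences in effectiveness between individuals receiving TES and CT over time".

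**Error control.** The only multiplicity rule is a 10% false discovery rate for the Aim 3 models. No alpha, either/both rule or ordering is given for the effectiveness tests.

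**The concern.** The two labels lead to different reports of the same data. If PHQ-9 shows no difference and GAD-7 does, one set of sections makes that a positive primary outcome and the other a secondary signal beside a null primary. The choice could be made after the results are known, and either choice could cite the plan.

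The two scales need not agree. Entry is on depression and/or anxiety, and each model uses only the patients who meet that scale's threshold, so the two tests rest on partly different patients. The secondary outcomes leave a similar choice between quality of life and suicidal ideation.

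**Working it through.** **Labels side by side**

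| Place | PHQ-9 | GAD-7 | PedsQL | Suicidal ideation |
|---|---|---|---|---|
| Protocol, Sub-aim 2.1 | primary | primary | secondary | not listed |
| Protocol, assessment strategy and Table 1 | primary | primary | secondary | not listed |
| Protocol, Aim 3 analysis | primary | primary | – | – |
| Protocol, Data Analysis, Effectiveness | primary | secondary | not named | secondary |
| SAP | primary | secondary | not named | secondary |

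The protocol disagrees with itself, so ranking the SAP above the protocol, or the reverse, would not remove the conflict. The textual finding needs no arithmetic. The rest shows its size.

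**Inputs from the documents.** 50 CT and 80 TES; a PHQ-9 difference of 3.1 at SD 5, so effect 3.1/5 = 0.62 (both from the effectiveness Power paragraph); effective sample size 112 (Aim 3 Power paragraph); patient-level randomization (RCT Enrollment Timeline); and/or entry.

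**Assumptions.** Two-sided 0.05 per scale; one contrast per scale; a two-sample z-test in place of the planned mixed model; a share q = 0.8 of patients qualifying for each scale; correlation rho of 0.3, 0.5, 0.7 or 0.9 between scales within a patient.

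**Correlation of the two tests.** Every patient meets at least one criterion, so the share in both models is 2q − 1 = 0.6. The test statistics then correlate at rho × (2q − 1)/q = 0.75 × rho, which is 0.225, 0.375, 0.525 and 0.675.

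**No true effect** (does not depend on sample size)
- P(GAD-7 significant, PHQ-9 not) = 0.05 − P(both significant) = 4.6%, 4.4%, 4.0%, 3.5%. This is two-sided. Half of it favours TES: 2.3%, 2.2%, 2.0%, 1.7%.
- Either counts: 0.10 − P(both significant) = 9.6%, 9.4%, 9.0%, 8.5%. With independent tests it is 1 − 0.95² = 9.75%.

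**Effect 0.62 on both scales**
- Effective n 112: 112 × 0.8 = 89.6, split 34.5 and 55.1; SE = √(1/34.46 + 1/55.14) = 0.2171; mean of each statistic 0.62/0.2171 = 2.86. P(GAD-7 only) = 13.3%, 12.0%, 10.4%, 8.6%.
- No clustering: 130 × 0.8 = 104, split 40 and 64; SE = √(1/40 + 1/64) = 0.2016; mean 0.62/0.2016 = 3.08. P(GAD-7 only) = 10.3%, 9.3%, 8.2%, 6.8%.
- Sensitivity to q at effective n 112: 8.4% to 3.3% if everyone is in both models; 16.4% to 12.4% if 70% qualify.

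**The case against.** **It is a pilot.** Aim 2 is to pilot feasibility, and the protocol says power did not set the sample size. Asking for a success rule could therefore impose confirmatory standards that the plan never claimed. This stands as a limit on severity. It does not remove the conflict: effectiveness is a named sub-aim, the plan tests for differences on these scales, and it speaks of primary analyses. If only estimates are intended, the documents should say so.

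**The calculation is not the planned analysis.** This also stands. A single-contrast z-test replaces a repeated-measures model with multiple imputation and possible propensity adjustment. The qualifying share is assumed, and effective n 112 comes from a cluster calculation although patients are randomized individually. The figures are illustrations, and the no-clustering case is given for that reason.

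**The documents are less silent than they look.** Partly right. The power statement refers to a PHQ-9 difference after treatment, and the moderation models use end-of-treatment scores, which Table 2 places at week 8. A reader might infer that no time point is given anywhere; that goes too far. What is missing is the time point or contrast for the main effectiveness model. Likewise, the suicidality procedures name PHQ-9 item 9, a Beck Depression Inventory item and the Columbia scale. They serve as safety tools there, and none is designated as the outcome measure.

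**Stronger readings that do not hold.** A reader might infer that the plan inflates the type I error. It does so across the two scales only if both are primary and either one suffices, which no section states. A reader might also infer from the roughly 114 participants in the PHI section that 88% of the trial had finished. That figure counts participants lacking a zip code, all of whom had completed. It is not the total completed, and it does not show that results by arm had been seen.

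**Conclusion.** The point holds as a contradiction between stated rules: GAD-7 is primary in three parts of the protocol and secondary in the protocol's analysis section and the SAP, with no governing label and no success rule. The secondary outcomes conflict in the same way, and the main contrast is not pinned to a time point.

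Under the stated assumptions, a false GAD-7-only claim of benefit has a chance of about 2.3% to 1.7%. Two-sided family-wise error is about 9.6% to 8.5% (at most 9.75% with one contrast per scale) if both are primary and either counts. At a true effect of 0.62 on both scales, a GAD-7-only result occurs about 13% to 9% of the time with effective n 112, or 10% to 7% without clustering. That last range measures how often the label would be disputed; with a real effect it is not a false-claim rate.

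In a pilot the harm is ambiguous labelling and selective emphasis. It should be fixed, but it does not invalidate the trial.

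**What to change.** Before results by arm are seen, use one hierarchy in Sub-aim 2.1, the assessment strategy with Table 1, the Data Analysis section, the Aim 3 analysis and the SAP. Name the contrast or time point it applies to, and the alpha if a test is to support a claim. The documents do not settle which hierarchy was meant, so the sponsor must choose:

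- **PHQ-9 sole primary, GAD-7 secondary.** This matches the Data Analysis section, the SAP and the only effect size given. It costs no PHQ-9 power. Patients who entered on GAD-7 alone fall outside the primary analysis: 0.2 × 130 = 26 if 80% meet the PHQ-9 criterion.
- **Both primary.** This matches the other three places and the and/or entry rule. State whether either counts, with Holm at an overall two-sided 0.05, or both are required. In the illustration with effective n 89.6 and effect 0.62, PHQ-9 power falls from about 0.81 to 0.78–0.79 under Holm if both scales respond, and to 0.73 if only PHQ-9 does. Requiring both gives joint power of 0.68 to 0.73.

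If only pilot estimates with no success claim are intended, say so under either option. Align PedsQL and suicidal ideation between Table 1 and the analysis text, and either name the suicidal-ideation outcome measure or remove that outcome.

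The protocol expected primary analyses by March 31st, 2024. If results by arm have already been seen, date the decision and report both scales with equal prominence, adding Holm-adjusted p-values if any success claim is made. The direct cost is wording in five places.

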Sub-aim 2.2 Implementation. Implementation targets will include reach (number eligible, treatment uptake, treatment completion) and cost.

Sub-aim 2.3 Optimization. We will use quality improvement methods³² to continuously improve the technology, service protocol (e.g., intervention and coordination protocols), and implementation plan.

Aim 3. Experimental Therapeutics Aims. We hypothesize that the impact of core UCD targets (usability, usefulness, and satisfaction) in the TES will result in increased objective and subjective markers of engagement relative to the CT, with improved downstream effects on depression. We also hypothesize the moderating effects of patient characteristics on engagement and depression will be lower levels in the TES arm, relative to CT, as a result of inclusion of users' voices through the design and optimization processes.

This project will result in the first TES for depression that can be successfully implemented in primary care and family medicine clinics. It will be achieved by creating tools that fit into the fabric of patients' lives by harnessing personal sensing.

BACKGROUND

Primary care is the de facto setting for depression and anxiety treatment for the majority of people.^{7,37-39} However, patient outcomes in primary care are extremely poor due to failure to identify symptoms, suboptimal treatment, and treatment access barriers.⁴⁰⁻⁴² Digital mental health strategies have been used to address depression and anxiety in primary care.

Technology-enabled services (TESs; which we define as a remotely delivered clinical service supported by digital tools and/or applications along with a human coach) offer the potential for adaptable psychological services that can be delivered more efficiently at scale that is not feasible for in-person services. Today, 81-85% of Americans own a smartphone, among whom 95% almost always have their phones with them.^{47,48} Rates are similar across racial and ethnic groups.⁴⁹ RCTs consistently show that TESs, when coupled with low intensity coaching, are highly effective for depression.^{50,51}

However, evidence is emerging that implementation efforts of TESs in real world healthcare systems have failed.^{14,15,16-18} Patients do not use the technologies, and TESs do not fit into the workflow of staff and providers. Simply put, current generation TESs do not engage patients or providers. Patients become frustrated and stop answering reminder calls.^{16,17}

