Additional data will be collected to evaluate intervention use, usability, satisfaction, and engagement. Measures of discrimination and stigma will be administered. Patient self-report measures have been uploaded to the eirb+ system for review. See data collection packets containing the measures to be administered via REDCap at screening, baseline, week 4, week 8, and week 12.

Assessment Strategy for Sub-aim 2.2 Implementation

Reach will be measured as follows: 1) Number of eligible patients will be the number of patients with PHQ-9 \geq 10 at a clinic visit during the study recruitment period; Treatment uptake will be the number of patients consented and randomized; 3) Treatment completion will be the number of patients completing at least 6 weeks of the 8-week treatment.

STU#:00211887

Optional Usability/User-Feedback Interviews (4w, 6w, 8w)

Participants will be informed during the informed consent process that they may be invited to complete optional interviews. All interviews will be conducted by telephone. At the end of the week 4 self-report survey, participants will be asked if they would like to provide additional feedback about their experience using the Vira app and working with the study coach via paid interviews. Participants who express interest in providing feedback will be contacted by study staff to schedule the optional interview session(s). More information about the nature and timing of the optional interviews is provided below.

Vira app usability interviews (4w, 6w, 8w)

As we begin enrolling the clinical trial, we will invite the first participants randomized to the TES condition to provide feedback on the usefulness and usability of the Vira application. These optional interviews will be administered to approximately 10 participants.

The app usability interview guide has been uploaded to the eirb+ portal for review.

Coaching user feedback interviews (4w)

All participants randomized to the TES will be invited to share additional user feedback about their experience working with the study coach at the week 4 (mid-treatment) timepoint.

The coaching user feedback interview guide has been uploaded to the eirb+ portal for review.

Failure to Initiate Treatment

If a participant fails to initiate treatment or fails to continue with treatment but is still engaged with the study, a single question survey will be administered to gauge the reason why they decided to not engage with the treatment.

Optional Focus Group (Post-Trial)

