RCT Timeline of Participant Activities

Active participation will last 12 weeks for each study participant. Participants will use the study apps and receive coaching (group 1 only) for the first 8 weeks. We will unobtrusively track all communication with the study coach. Assessment will continue through week 12. Study assessment milestones are laid out in tables 3 and 4 below.

Table 2. Online surveys to be administered to all participants

Method	Week 0	Week 4 Mid-Treatment	Week 8 End of Treatment	Week 12 Post-Treatment
Self-report Survey	x	x	x	x
App Usage	Continuous, unobtrusive			

Table 3. Optional interview data to be collected from patients randomized to TES

Method	Week 4 Mid-Treatment	Week 6	Week 8 End of Treatment
Vira app usability interview	x	x	x
Coaching user-feedback interview	x		

Table 4. Optional focus group be completed with patients randomized to control and TES

Method	Post-Trial Completion
Focus Group (semi-structured interview guide)	x

The anticipated completion date for primary analyses is March 31st, 2024.

RCT INCLUSION AND EXCLUSION CRITERIA:

Trial participation will be offered to patients at Rush University Medical Center aged 13 or older. Children under the age of 13 will be excluded given likely differences in development and

STU#:00211887

smartphone ownership that would make such young children an inappropriate population for evaluating the technology enabled service and implementation plan.

Inclusion Criteria: US Citizen/Resident (for payment purposes) living in the US during the 12-week study period (for tech functionality, data security, and safety management purposes), 13 years or older (if age 13-17, parent/caregiver must provide consent, a consent process is in place for English-speaking minors with Spanish-speaking parents), English speaking, eligible to receive care through Rush University Medical Center or its clinical affiliates, owns an Android or iPhone smartphone with an up-to-date operating system, has used a smartphone in the last 7 days, at least moderate symptoms of depression (PHQ-9 greater than or equal to 10) and/or anxiety (GAD-7 greater than or equal to 8)

Exclusion Criteria: Severe suicidality (as defined by presence of a plan + intent to act on that plan)

VULNERABLE POPULATIONS

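### The multiple-imputation plan names no auxiliary variable; a short app-use summary, already logged in both arms, should be added in case survey dropout follows disengagement

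*SAP*

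**What the plan says.** The SAP's whole treatment of missing data is one sentence: "Missing data will be managed through multiple imputation". The protocol repeats it under Data Analysis, Effectiveness (Sub-Aim 2.1). Neither text lists imputation variables, states a missingness assumption or plans a sensitivity analysis. The main comparison is a GLMM over time, run separately for PHQ-9 and GAD-7.

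The protocol describes a record that does not need the patient to answer a survey. RCT Procedures Involved states "App use will be tracked for the entire study duration". Table 2, which covers all participants, lists app usage as "Continuous, unobtrusive". The vendor table under Data Management and Confidentiality shows app-use events held for both the Vira app and the control app. For the coached arm the protocol adds "We will unobtrusively track all communication with the study coach".

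In the analysis text, app use appears only in Aim 3: "objective engagement will be measured by app use (number of app launches and time from first to last use", with the hypothesis "We hypothesize that the difference between the TES and CT will be mediated by subjective and objective engagement".

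**The concern.** A GLMM fitted by likelihood already handles missing PHQ-9 and GAD-7 scores under missing-at-random given the variables in the model. Imputing those scores from the same variables makes the same assumption and, in large samples, gives essentially the same answer. For the outcomes in the main comparison, imputation gains mainly through information the GLMM does not hold.

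App use is the natural candidate. The protocol hypothesises that engagement differs by arm and affects outcome, and only TES has a coach whose tasks include app engagement. If disengaged patients do worse and also skip surveys, the responders in each arm look better than the arm as a whole. If that happens more in the control arm, the control mean is flattered most and the TES-CT difference shrinks.

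**Working it through.** **Plan's own figures.** The documents give no dropout rate and no use-outcome correlation, so there is no missing-data figure to reproduce. Two planning figures serve as a yardstick (protocol, Power paragraph under Sub-Aim 2.1): effect size 0.62 and SD 5, so 0.62 × 5 = 3.1 points, as stated. The power attached to 0.62 depends on an unstated number of clinics and plays no part here. With the 80 TES and 50 CT patients of that paragraph, ignoring dropout, clustering and baseline adjustment:

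SE = 5 × √(1/50 + 1/80) = 5 × √0.0325 = 0.90 points.

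**Assumed model.** The true week-8 difference is −3.1. Disengagement Z is standard normal. Its correlation with the week-8 score is r, and its link to the week-4 score is 0.4 of that; it is unrelated to baseline. The log-odds of dropout rise by 1 per SD of Z, or by 0 where disengagement does not drive dropout. The app log correlates 0.5 or 0.9 with Z.

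**Hand check.** Among responders the mean of Z is m = E[Z·q(Z)] / E[q(Z)], with q the response probability calibrated to the dropout rate. This gives m = −0.133, −0.253 and −0.332 at 15%, 30% and 40% dropout. Bias in the complete-case difference is 5 × r × (m_TES − m_CT).
- r = 0.4, dropout 30% CT and 15% TES: 5 × 0.4 × (−0.133 + 0.253) = 0.24.
- r = 0.4, dropout 40% CT, disengagement driving dropout in CT only: 5 × 0.4 × 0.332 = 0.66.

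The simulation's complete-case biases agree: 0.24 to 0.25, and 0.65 to 0.66.

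**Imputation by arm, large samples (400,000 per arm).** The entries are bias in the difference, toward no effect. Where two values are joined by a slash, the log correlates 0.5 / 0.9 with disengagement.

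| r | Dropout CT/TES | Disengagement drives dropout in | Without log (baseline + week 4) | With log |
|---|---|---|---|---|
| 0 | 30%/15% | both arms | 0 | 0 |
| 0.4 | 20%/20% | both arms | about 0 | about 0 |
| 0.2 | 30%/15% | both arms | 0.11 | 0.08 / 0.03 |
| 0.4 | 30%/15% | both arms | 0.21 to 0.22 | 0.16 / 0.06 |
| 0.4 | 20%/20% | CT only | 0.30 | 0.23 / 0.07 |
| 0.4 | 40%/20% | CT only | 0.56 to 0.57 | 0.45 / 0.11 |

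For example, in the last row the 0.5 log moves the estimate from −2.54 to −2.66 against a true −3.11. The bias falls from 0.57 to 0.45, so 0.12/0.57 = 21% is removed. The 0.9 log takes it from 0.56 to 0.11, so 0.45/0.56 = 80% is removed. The week-4 score removes little: 0.66 falls only to 0.57.

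**At the trial's size (50 CT, 80 TES).** With assumed dropout of 35–40% in CT and 15–20% in TES, bias was 0.13–0.29 without the log and 0.02–0.11 with one use summary entered by arm. The SD of the estimate rose 1–7% and the root mean squared error 0–3%. A longer auxiliary list raised the root mean squared error by 2–6%.

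No separate calculation was made for GAD-7; the argument is the same.

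**The case against.** Several points against this stand.

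- **Silence is not exclusion.** A reader might infer that the trial plans to impute without app use. The plan names no imputation variable at all, so the supportable finding is that app use is not named.
- **The protocol does not say that survey non-response will follow disengagement.** The remark "Patients become frustrated and stop answering reminder calls" comes from the Background and concerns earlier services. Under Failure to Initiate Treatment, the protocol foresees a patient who "fails to continue with treatment but is still engaged with the study". Surveys run in REDCap rather than in the apps, with telephone as fallback. Each pays $25 in both arms, and follow-up is permitted after voluntary withdrawal from treatment. All of this weakens the link.
- **App use is not the only passive record.** Coach communication and phone sensor data also accumulate, though in TES only. App use is the engagement record described for both arms.
- **Imputation is not pointless without app use.** It can also supply missing moderators, covariates and end-of-treatment scores for the single-time-point moderator models.
- **App use may be a weak proxy.** Vira is designed to need little user effort, so few launches need not mean disengagement. A simulation in which the log itself drives dropout would show nearly all the bias removed, but that result is circular.
- **The gain is in bias, not overall accuracy.** At 35% dropout only about 50 × 0.65 ≈ 32 control patients respond, and the root mean squared error does not improve.

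What remains is a specific gap. The plan leaves the imputation model open, and the protocol's own mediation hypothesis identifies a variable that belongs in it.

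**Conclusion.** The point holds as a low-cost improvement. Across the assumed scenarios in which disengagement predicts outcome and dropout differs by arm in rate or mechanism, imputation without app use leaves about 0.1 to 0.6 PHQ-9 points of bias toward no effect. That is at most about two thirds of one standard error (0.57/0.90 = 0.63), and 0.11/3.1 = 4% to 0.57/3.1 = 18% of the planning difference. If disengagement is unrelated to outcome, or dropout rate and mechanism match across arms, bias in the difference is about zero. Equal dropout rates alone are not enough. The direction assumes that the control arm loses more of its disengaged patients; the reverse pattern would change the sign.

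App use would remove roughly a fifth to four fifths of the bias in the worked cases. A reader might conclude that the planned comparison is biased, or that app use would fully correct it. The documents support neither, because dropout and the strength of the app-use link are unknown.

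**What to change.** Specify the imputation model in the SAP:
- Impute separately by arm, because the two apps differ and their use counts are not comparable.
- Beyond baseline and the repeated outcome scores, add one or two pre-specified app-use summaries, for example launches per 4-week period or time of last use. Count patients who never open the app as zero use, not as missing.
- Keep these variables out of the analysis GLMM. Use is post-randomisation and a hypothesised mediator, so adjusting for it would change the intention-to-treat contrast.
- Report imputation without app use as a sensitivity analysis.

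The cost is SAP wording and a merge of app logs with survey data; nothing new is collected. The statistical price is a few percent more variance at this sample size, which is why the auxiliary list should stay short. If the primary analysis has already been run, report the model with app use as a labelled sensitivity analysis instead.
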